1.0 Objectives / Specific Aims

- Objectives: To determine the feasibility and safety of using this assistive device, TheraBracelet, every day during waking hours, and to determine if TheraBracelet's instant effects are sustained during prolonged use.
- Design: Community-dwelling chronic stroke survivors will be randomly assigned to either the treatment or control condition for the first month, followed by a 2-week washout period and then crossover to the other condition. In both the treatment and control conditions, participants will be instructed to wear the device for at least 8 hours/day every day during their normal daily activity and come to the laboratory for evaluation prior to and each week of using the device (for a total of 5 evaluations over 4 weeks). The device will deliver vibration (treatment) or no vibration (control). Double-blinding will be possible because the treatment vibration is imperceptible (i.e., subthreshold).
- Primary Aim: Determine the feasibility and safety of using TheraBracelet daily for a month. For feasibility, compliance in using the device will be assessed by weekly self-reports of usage. Hypothesis: TheraBracelet will have a feasibility level comparable to wearing a non-vibrating wristband. To determine safety, participants will be examined at each weekly visit for any worsening of hand sensation, dexterity, grip strength, upper limb pain, spasticity, and wrist skin irritation. Adverse events will be recorded and categorized by severity (minor, moderate, and serious) and device relevance (related to device use or not). Adverse event frequency will be compared between conditions, and with a comparable FDA-approved device, Bioness electrical muscle stimulator. Hypothesis: TheraBracelet will have a safety level equivalent to or better than the comparable FDA-approved assistive device.
- Secondary Aim: Determine the durability of TheraBracelet's instant effect over a month. TheraBracelet's instant effects will be quantified as an increase in the hand touch sensation score, dexterity score, and grip strength with vibration turned on vs. off (with 'on' and 'off' tested in a random order) in each weekly evaluation. Hypothesis: TheraBracelet's instant effects in improving hand function will persist across all weekly evaluations (i.e. desensitization to vibration will not occur during extended daily use over a one-month period). In addition, the broader impact of TheraBracelet will be assessed by comparing self-reported abilities for activities of daily living and quality of life between the treatment and control conditions.

2.0 Background

Stroke is a leading cause of long-term disability in the U.S. More than two thirds of nearly 7 million stroke survivors in the U.S. have persistent hand impairment. This treatment-resistant hand impairment diminishes stroke survivors' abilities for activities of daily living including self-care, hygiene, and employment, which lowers their independence and burdens caregivers. The total cost of stroke from 2005 to 2050 is projected to be \$2.2 trillion, with \$13 billion annually in indirect costs associated with lost wages.

Unfortunately, with the rehabilitation service reimbursement cap, most stroke survivors live with persistent hand impairment for the rest of their lives, with no therapy. Existing devices are impractical for daily home use. The proposed technology aims to fill this gap by providing an assistive device, TheraBracelet, that enhances stroke survivors' hand sensation and dexterity throughout daily living. Our preliminary studies with this vibrating

wristband have shown to instantly improve chronic stroke survivors' touch sensation as well as hand dexterity (Enders et al. 2013; Seo et al. 2014). However, additional research is needed to evaluate the feasibility and safety of TheraBracelet over longer periods of time (e.g. one month) as well as durability of its instant effect. Public health implication is that by improving stroke survivors' abilities for activities of daily living, TheraBracelet intends to increase functional independence and lessen caregiver burdens, which will contribute to increased rates of return to work and productive lifestyle for both stroke survivors and caregivers.

3.0 Intervention to be studied

Device: A stand-alone prototype is composed of an MP3-playing watch and a vibrator (see the pictures below; total weight 40g, watch=3.7cm×5.3cm). Both items are off-the-shelf products (i.e. available to purchase for anyone). The vibrator is attached to the wristband of the watch. The vibrator's wire is connected to the MP3 player via an audio jack. The MP3 player drives the vibrator with its internal battery for at least 22 hours, enabling a full day of use after an overnight charge. The MP3 player/watch is charged using a conventional phone charger. The MP3 player can play any file including the treatment vibration file with white noise vibratory signal at the intensity that is 40% below the sensory threshold (i.e. subthreshold, imperceptible to the participant) and control file with zero amplitude (i.e. no vibration).

FDA: The use of the vibrator for this proposed purpose of affecting the hand sensation and/or dexterity has not been approved by the FDA. The vibrator is a general-purpose vibrator, not specifically designed for any particular purpose. Safety of using this vibrator at the proposed intensity (40% below the person's sensory threshold, i.e. imperceptible) for a month has not been studied, and will be studied as a primary aim of the proposed research. Currently there is no vibration exposure guideline for this small level of vibration. People are exposed to higher-intensity, suprathreshold vibration daily (e.g. from a phone, riding a car).

Control/placebo: No vibration will be the control condition. The MP3 player will play a zero-amplitude file, producing no vibration.

4.0 Inclusion and Exclusion Criteria/ Study Population

Inclusion Criteria

- Age = 18 or older
- Time since stroke > 3 months
- Those with at least some movement in the affected upper limb (The Fugl-Meyer upper limb score is expected to be approximately 20 or higher)
- Able to put on the device at home
- Ability to perform the Box and Block Test with a score greater than zero

Exclusion Criteria

- Comorbidity such as peripheral neuropathy, orthopaedic conditions in the hand
 - Compromised skin integrity of the hand/wrist due to long-term use of blood thinners, scars on the hand/wrist from burn or other injury
 - Participation in an upper limb rehabilitation program concurrently
 - Pregnancy, since swelling is common in pregnancy
 - Those whose swelling changes dramatically during the day, which would require constant adjustment of the wristband tightness
 - Participant has received Botulinum toxin injection in the past 3 months
 - A language barrier or cognitive impairment that precludes following instructions
 - Inability or unwillingness of subject or legal guardian/representative to give informed consent
-
- Screening: Eligibility will be determined based on the potential participant's verbal disclosure.
 - Exclusion of children: Children will not be recruited since stroke is rare in children.

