- **Feasibility:** We will compare user compliance in using the device in the treatment vs. control. Compliance will be assessed using self-reports. Participants will bring home a device usage log, record time at which they put on and take off the device every day, and submit the log during the weekly evaluation. Study personnel will record which hand the participant is wearing the device (right vs left) at the beginning of the weekly evaluation session. During their final session, participants will complete a technology acceptance questionnaire to evaluate their experience using the device. Additionally, a pedometer function will be run in the watch to obtain a total number of steps for a week, which can provide a rough estimate of the wear time. Participants will also wear the device while completing a 10-meter walk test during their initial visit. Walking speed and the pedometer reading will be recorded when the test is complete.
- **Safety:** We will compare the rate of occurrence of adverse events in the treatment vs. control condition. The measures of adverse events will include worsening of hand sensation, hand strength, hand dexterity, upper limb pain level, spasticity, and wrist skin irritation. Specifically, hand sensation will be assessed using the Monofilament Test, the Two-Point Discrimination Test, and verbal report of any numbness and tingling. Hand sensation will be determined to have deteriorated if any of these hand sensation test results declines by a category (e.g. "normal" to "diminished light touch" for the Monofilament Test with a change more than two points; "no" to "yes" for numbness and tingling). Hand strength will be determined to have deteriorated if grip strength declines by more than 20% from the baseline (which is approximately 2 standard deviation of the population grip strength data) and more than minimal

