detectable change (MDC) (also known as the smallest real difference, Chen et al 2009). Hand dexterity will be determined to have deteriorated if the Nine Hole Peg or Box and Block Test score worsens by more than 20% (approximately 2 standard deviation of the population data) and MDC (Chen et al 2009). Hand strength and dexterity measurement will be performed three times during the baseline testing. Upper limb pain will be assessed using the visual analog pain rating scale (0 to 10). Upper limb pain will be determined to have increased if the pain level indicated on the visual analog pain rating scale increases by more than 2. Spasticity will be show assessed using the Modified Ashworth Scale (MAS). Spasticity will be determined to have worsened if MAS increases by more than 1 point (equivalent to the effect size of botulinum toxin A). Wrist skin irritation and increased swelling, if there is any, will be noted. Rigorous safety criteria will be used in which adverse events will be noted if any of the measures (hand sensation, strength, dexterity, pain, spasticity, skin irritation, swelling) worsens at any of the four evaluation times compared to the baseline. The co-investigator and study neurologist, [name], will meet with each participant in person or via teleconference to interview the participant regarding safety related to wearing the device.

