11.0 Provisions to Monitor the Data to Ensure the Safety of Subjects

- Data and Safety Monitoring Board (DSMB): The primary purpose of the DSMB is to ensure the safety of participants and the validity and integrity of data collected during the study. By having the DSMB, safety concerns will be addressed objectively, in a timely manner. If the intervention definitively has safety concerns, the DSMB may recommend stopping the study early.
- The DSMB will be composed of (1) a board certified physician with expertise in stroke management, (2) a registered and licensed occupational therapist with expertise in stroke rehabilitation, and (3) a biostatistician with expertise in design and analysis of clinical trials.
- The responsibilities of the DSMB are as follows. Prior to any enrollment, the DSMB will review the study design, protocol, recruitment/enrollment plan, statistical analysis plan, and data safety monitoring plan, and document the agreement or recommendation. Once the enrollment begins, the DSMB will convene every 3 months to review the safety data (i.e. worsening of hand sensation, hand strength, hand dexterity, upper limb pain level, upper extremity spasticity, and wrist skin irritation, and any other adverse events regardless of whether it is related to the device use or not) as well as the enrollment data including any discontinuation of participation in the study with or without adverse events, new enrollments, and progression of the enrollees' participation in the study. The DSMB will review the aggregated summary data as well as the individual participants' data (de-identified). The DSMB will provide recommendations for any adverse events and safety concerns. The DSMB will also provide a report to the IRB to summarize oversight activities, recommendations, and any concerns regarding participant safety.
- The DSMB will have access to coded (de-identified) data but not identifiable data. While the experimenters and participants are double-blinded to the condition assignment information during the study progression, the DSMB will have access to the condition assignment information during the study progression in order to assess

the safety of the TheraBracelet vibration in comparison to that of simply wearing a wristband (i.e. control) and separately assess other safety issues such as assessments.

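### Box and Block worsening must exceed both 20% and the MDC, yet entry needs only a score above zero, so a low-baseline participant can fall to zero without a Box and Block event

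*Combined protocol and SAP*

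**What the plan says.** Section 4.0 lists as an inclusion criterion "Ability to perform the Box and Block Test with a score greater than zero". The same list expects a Fugl-Meyer upper limb score of roughly 20 or more. No higher Box and Block minimum is set, and ability to do the Nine Hole Peg Test is not an entry requirement.

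Section 9.0 (Safety) defines deteriorated dexterity through either of two tests, the Nine Hole Peg or the Box and Block. The condition is that the "score worsens by more than 20% (approximately 2 standard deviation of the population data) and MDC". The grip-strength rule just before it has the same two-part form, which supports reading both parts as required. The MDC is given only by citation to a test-retest study in stroke, with no number and no unit. Strength and dexterity are measured three times at baseline.

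The composite is broad: "adverse events will be noted if any of the measures (hand sensation, strength, dexterity, pain, spasticity, skin irritation, swelling) worsens" at any of the four later evaluations. Section 11.0 also has the DSMB review "any other adverse events regardless of whether it is related to the device use or not".

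Under Schedule in section 9.0, a later follow-up assessment takes place only when a safety measure has met the adverse-event definition by the tenth visit, and it covers only that measure.

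The plan has no rule for a Box and Block baseline at or below the MDC, for a score of zero after baseline, or for a peg test that can no longer be completed.

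**The concern.** The MDC condition keeps measurement error from being counted as harm. Joined by a logical and to a percentage, and applied to a population with almost no entry floor, it also has an effect that the plan does not discuss. In the weakest eligible hands the largest possible Box and Block loss may be too small to count, while a much smaller proportional loss counts in a stronger hand.

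Safety is a primary aim, tested for non-inferiority against the same participants' control month. If a participant cannot register a given kind of event in either month, a real excess on treatment shrinks toward zero, which is the direction that supports a conclusion of safety. Section 10.0 also gives a count rule with its boundary at three of 24 participants, so one participant whose only event went uncounted could move the tally from four to three. An uncounted Box and Block loss would not trigger the follow-up assessment either.

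**Working it through.** **Inputs.** The entry floor is any score above zero, so 1 block or more (section 4.0). The event rule is a fall of more than 20% and more than the MDC (section 9.0). The MDC value and unit are not in the documents. I assume an absolute block count and show 3, 5 and 8. I also assume whole-block scores, since the plan does not say how the three baseline measurements are combined.

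**The plan's own figures.** The only number in the rule is 20%. The sample size of 24 does not depend on this point. With margin 0.20, discordance 0.10 and no true difference, an exact calculation for the restricted-likelihood score test at one-sided 5% gives 82% power at 24, consistent with the stated 80%.

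**Step 1: can an event occur?** With baseline B and MDC M, the largest possible fall is B. An event needs a fall above M, so none is possible when B ≤ M:

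- M = 3: baselines 1–3
- M = 5: baselines 1–5
- M = 8: baselines 1–8

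Under the 20% condition alone, each of these falls to zero would be a 100% decline and would count.

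**Step 2: which condition sets the threshold?** The 20% condition is the stricter one only when 0.20 × B > M, that is when B > 5M. This means above 15, 25 or 40 blocks for M = 3, 5 or 8.

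**Step 3: smallest whole-block fall that counts.** This is the smallest whole number greater than both 0.20 × B and M.

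| Baseline | 20% alone | M = 3 | M = 5 | M = 8 |
|---|---|---|---|---|
| 5 | 2 (40%) | 4 (80%) | impossible | impossible |
| 8 | 2 (25%) | 4 (50%) | 6 (75%) | impossible |
| 10 | 3 (30%) | 4 (40%) | 6 (60%) | 9 (90%) |
| 15 | 4 (27%) | 4 (27%) | 6 (40%) | 9 (60%) |
| 20 | 5 (25%) | 5 (25%) | 6 (30%) | 9 (45%) |
| 40 | 9 (22.5%) | 9 (22.5%) | 9 (22.5%) | 9 (22.5%) |

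**Step 4: effect on the comparison.** Suppose a share f of participants had no route at all to an event. A true excess of 20 percentage points would then appear as 20 × (1 − f): 20 at f = 0, 18 at f = 10%, 15 at f = 25%. The share f is assumed, and these figures overstate the dilution from this defect because other routes to an event exist.

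**The case against.** A reader might infer that a participant can lose all hand dexterity with no adverse event recorded. The documents do not support that. The peg test is an alternative route to a dexterity event and its time score does not have this floor. Worsening in sensation, strength, pain, spasticity, skin or swelling also counts. The study neurologist interviews each participant about safety, and the DSMB sees individual data and adverse events of any kind. What remains is that completing the peg test is not required at entry, so some participants may lack that route, and the plan does not say how a newly uncompletable peg test is scored. Events in other domains do not repair the dexterity definition.

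The absolute unit is an inference. If the MDC were a percentage of baseline below 100%, a fall to zero would exceed it and Step 1 would fail. Against that, if both conditions were fixed percentages, one would always be redundant, so the two-part rule makes sense mainly with an MDC in test units.

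No baseline distribution is given, so the number of the 24 participants affected may be zero. This stands.

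The MDC also has a proper purpose. If it exceeds 2 blocks, a fall from 2 to 0 is within measurement error by the plan's own standard, and counting it may add false positives. This stands as a cost of the fix.

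A reader might extend the argument to grip strength because the rule has the same form. The documents give neither a minimum grip nor a grip MDC, so there is nothing to support that extension.

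**Conclusion.** The point holds for the Box and Block component of the dexterity event. Given an absolute MDC, an eligible participant with a baseline at or below it can fall to zero without a Box and Block event. Above that baseline, up to about five times the MDC, the working threshold is the MDC rather than the stated 20%. At a baseline of 10 blocks the required fall is 40%, 60% or 90% for an MDC of 3, 5 or 8.

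It matters most for participants who cannot do the peg test at baseline. Any bias in the primary safety comparison is toward non-inferiority, but its size cannot be computed from the documents. The point does not show that the safety conclusion would be wrong, and it leaves the sample size unchanged. It rests on two assumptions: that the MDC is in blocks, and that it lies in the range shown. The missing value and unit are themselves a gap in a primary endpoint definition.

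**What to change.** In the Safety text of section 9.0:

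1. State the MDC value and unit for each test that uses one.
2. Add that, when the Box and Block baseline is at or below the MDC, a score of zero on all attempts at a visit counts as dexterity worsening. Judge this with vibration off, against the three-measurement baseline, and state the number of attempts per visit. The plan tests with vibration on and off at each evaluation without saying which result feeds the safety comparison.
3. Add that inability at any visit to complete a Nine Hole Peg Test that was completed at baseline also counts as dexterity worsening.
4. Report the safety comparison with and without the events added by items 2 and 3.

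The cost is a few sentences, with no new tests and no change in sample size. A few falls within measurement error may be counted, in both conditions; requiring zero on every attempt limits this, and the paired reporting shows its effect. The fix does not change the rule for baselines just above the MDC. With an MDC of 5, a fall from 6 to 1 (5/6, 83%) would still not count, but stating the MDC makes that visible.

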5.0 Number of Subjects

The enrollment goal is 24 subjects at the time of randomization. Considering potential ineligibility after enrollment, a total of 30 recruitment is proposed.

7.0 Recruitment Methods

This study will recruit from the Registry for Stroke Recovery (RESTORE-Pro#00037803, IRB approved 9/6/14) which is a research tool sponsored by the National Institutes of Health (NIH) Center of Biomedical Research Excellence (COBRE) in Stroke Recovery with subjects consented for future contact to support stroke recovery research conducted at MUSC. RESTORE staff will query the registry for potential subjects and provide the Principal Investigator (PI) with the contact information of subjects who meet their criteria. The PI or research staff will contact subjects to further screen for potential enrollment.

8.0 Consent Process

Informed consent will be obtained from the participant. The consent process will take place when the potential participant comes to the laboratory on a scheduled time agreed upon between the study personnel and the participant. In a private room, the content of the consent will be verbally explained to the participant and the participant will be asked to raise any questions and concerns. If the person requests a waiting period, then one will be

given. If the person desires to consent immediately, then the person will provide consent immediately.

9.0 Study Design / Methods

- **Study design:** The study will use a 2×2 crossover design. Participants will be randomly assigned to either the treatment or control condition for the first month, followed by a 2-week washout period and then crossover to the other condition. For both conditions, participants will be instructed to wear TheraBracelet on the affected wrist every day for at least 8 hours/day during their daily activity over a month. The device will apply wrist vibration at 60% of the sensory threshold (imperceptible) for the treatment condition, and no vibration for the control condition. The control condition is needed to assess safety of TheraBracelet in comparison to that of simply wearing a wristband, thereby accounting for any worsening of symptoms that may occur as a natural course after stroke. Half the participants will start with the treatment and half with the control (balanced).
- **Schedule:** One person's participation will be 2.5 month long (= 1 month for one condition, 2 week washout period, 1 month for another condition). For each condition, participants will come to the laboratory once a week for evaluation for a total of 5 times: The 1st visit will entail the baseline evaluation followed by an introduction to using the device. Subsequent visits will be for evaluation after using the device each week. A follow-up assessment will be administered 4-16 weeks after the 10th session if any safety measure has worsened as defined as an adverse event by the 10th visit compared to the 1st visit. The follow-up assessment will evaluate only the measure that has worsened.
- Evaluation will include feasibility, safety, and durability, as detailed below.
- **Feasibility:** We will compare user compliance in using the device in the treatment vs. control. Compliance will be assessed using self-reports. Participants will bring home a device usage log, record time at which they put on and take off the device every day, and submit the log during the weekly evaluation. Study personnel will record which hand the participant is wearing the device (right vs left) at the beginning of the weekly evaluation session. During their final session, participants will complete a technology acceptance questionnaire to evaluate their experience using the device. Additionally, a pedometer function will be run in the watch to obtain a total number of steps for a week, which can provide a rough estimate of the wear time. Participants will also wear the device while completing a 10-meter walk test during their initial visit. Walking speed and the pedometer reading will be recorded when the test is complete.
- **Safety:** We will compare the rate of occurrence of adverse events in the treatment vs. control condition. The measures of adverse events will include worsening of hand sensation, hand strength, hand dexterity, upper limb pain level, spasticity, and wrist skin irritation. Specifically, hand sensation will be assessed using the Monofilament Test, the Two-Point Discrimination Test, and verbal report of any numbness and tingling. Hand sensation will be determined to have deteriorated if any of these hand sensation test results declines by a category (e.g. "normal" to "diminished light touch" for the Monofilament Test with a change more than two points; "no" to "yes" for numbness and tingling). Hand strength will be determined to have deteriorated if grip strength declines by more than 20% from the baseline (which is approximately 2 standard deviation of the population grip strength data) and more than minimal

detectable change (MDC) (also known as the smallest real difference, Chen et al 2009). Hand dexterity will be determined to have deteriorated if the Nine Hole Peg or Box and Block Test score worsens by more than 20% (approximately 2 standard deviation of the population data) and MDC (Chen et al 2009). Hand strength and dexterity measurement will be performed three times during the baseline testing. Upper limb pain will be assessed using the visual analog pain rating scale (0 to 10). Upper limb pain will be determined to have increased if the pain level indicated on the visual analog pain rating scale increases by more than 2. Spasticity will be show assessed using the Modified Ashworth Scale (MAS). Spasticity will be determined to have worsened if MAS increases by more than 1 point (equivalent to the effect size of botulinum toxin A). Wrist skin irritation and increased swelling, if there is any, will be noted. Rigorous safety criteria will be used in which adverse events will be noted if any of the measures (hand sensation, strength, dexterity, pain, spasticity, skin irritation, swelling) worsens at any of the four evaluation times compared to the baseline. The co-investigator and study neurologist, [name], will meet with each participant in person or via teleconference to interview the participant regarding safety related to wearing the device.

- **Durability:** The durability of TheraBracelet's instant effect will be examined by assessing TheraBracelet's instant effect in each weekly evaluation and comparing them across. The instant effect will be quantified as increase in the hand touch sensation (Monofilament Test) dexterity scores (Nine Hole Peg and Box and Block Tests) with vibration turned on compared to off, with the 'on' and 'off' tested in a random order, blinded, within a single evaluation session. If TheraBracelet's instant effect is seen for all evaluation times, it will support durability (i.e. desensitization to vibration does not occur). In addition, the impact of TheraBracelet on stroke survivors' self-reported abilities for activities of daily living and quality of life will be assessed. Specifically, the Stroke Impact Scale, SIS (sections of the hand, activities of daily living, and recovery), and Stroke Specific Quality of Life, SS-QoL (sections of the self-care and upper extremity function), will be obtained at weekly evaluations and compared between the two conditions. The Nine Hole Peg and Box and Block Tests will be videoed to ensure the exact start and stop time are recorded. This video will not include the participant's face in order to maintain confidentiality.
- **Protection against risk:** For fatigue, frequent sufficient breaks will be provided to participants. As for potential skin irritation due to wearing the wristband, the wristband tightness may be adjusted with a new wristband to maximize participant comfort. Participants will be notified if we learn anything that might make them change their mind about participating in the study. Potential risks of deterioration of hand sensation, strength, and dexterity, increased upper limb pain level and spasticity level, and/or wrist skin irritation will be monitored every week during the weekly evaluation when participants come to the laboratory. In fact, these events are the outcome measures of safety for the primary aim of the study. Participants will be informed that they can drop out of the study any time without penalty.

